12.1.5 1-Month Postoperative Visit (Visit 3A)

Visit 3A: 20-40 Days Post 2nd Eye Implantation, Binocular

Below is a list of study procedures to be undertaken at Visit 3A. It is recommended that procedures are performed in the order described below unless otherwise stated. All assessments must be documented in source documentation and case report forms (if applicable).

- 1. Record changes in medical/ocular history and ocular and non-ocular concomitant medications.
- 2. [REDACTED]
- 3. [REDACTED]
- 4. [REDACTED]
- 5. Assess binocular uncorrected distance visual acuity.
[Both Eyes, Binocular]
- 6. [REDACTED]
- 7. Assess binocular uncorrected near (40 cm) visual acuity.
[Both Eyes, Binocular]
- 8. [REDACTED]
- 9. Assess binocular uncorrected intermediate (60 cm) visual acuity.

[Both Eyes, Binocular]

10. Perform defocus testing.

[Both Eyes, Binocular]

11. Perform mesopic without glare contrast sensitivity testing.

[Both Eyes, Binocular]

12. Perform mesopic with glare contrast sensitivity testing.

[Both Eyes, Binocular]

13. Perform photopic without glare contrast sensitivity testing.

[Both Eyes, Binocular]

14. Perform photopic with glare contrast sensitivity testing.

[Both Eyes, Binocular]

15. Perform slit lamp examination of the anterior segment. Include documentation of IOL observations, if any.

[Both Eyes, Bilateral]

16. Observe any IOL position changes (ie, tilt and decentration) occurring since the previous visit.

[Both Eyes, Bilateral]

17. Assess subjective PCO, and record information for any posterior capsulotomy that has occurred since surgery, if applicable.

[Both Eyes, Bilateral]

18. Perform dilated fundus exam noting any issues with fundus visualization due to the lens optic.

[Both Eyes, Bilateral]

19. Perform tonometry to measure the IOP.

[Both Eyes, Bilateral]

20. Record any AEs including SSIs.

Note: SAEs including SSIs must be entered into EDC within 24 hours of the

Investigator's knowledge. Refer to Section 13 for further detail.

21. Record any device deficiencies. Refer to Section 13 for further detail.

12.1.6 6-Month Postoperative Visit (Visit 4A)

Visit 4A: 120-180 Days Post 2nd Eye Implantation, Binocular

Below is a list of study procedures to be undertaken at Visit 4A. It is recommended that procedures are performed in the order described below unless otherwise stated. All assessments must be documented in source documentation and case report forms (if applicable).

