15.4.1.2 Analysis Methods

The primary hypothesis will be tested by generating a two-sided 90% confidence interval using repeated measures analysis of variance at a type I error rate of 5%, 1-sided. Tests at each visit will be reported with Visit 4A (120-180 days) prospectively identified as the primary time point of interest. The upper bound of the two-sided 90% confidence interval will be compared to the margin, 0.1. If the upper bound is less than the margin, the null hypothesis will be rejected and the TFNT00 IOL will be concluded non-inferior to the 839MP IOL for UCIVA.

The two sided 90% confidence intervals will be reported for the difference between the treatment groups at each visit.

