15.4.2.2 Analysis Methods

For the superiority hypothesis tests, treatment group comparison for UCIVA will be made and the first secondary objective will be demonstrated if $p < 0.025$ from a repeated measures analysis of variance at a Type I error rate of 2.5%. Tests at each visit will be reported with Visit 4A (120-180 days) prospectively identified as the primary time point of interest. The two-sided 95% confidence intervals will be reported for the difference between treatment groups at each visit. For the fourth and fifth secondary objectives, superiority will be demonstrated if $p < 0.05$ (or $p < 0.025$, depending on the gatekeeping) for UCNVA and UCDVA at Visit 4A (120-180 days), respectively.

For the non-inferiority hypothesis test of UCDVA, the second secondary objective, treatment group comparisons will be tested by generating a two-sided 95% confidence interval from a repeated measures analysis of variance, with site included as a covariate, at a Type I error rate of 2.5%. The variable 'visit' will be entered as a classification variable to avoid assumptions on the shape of the response and least squares means will be used to estimate the treatment effect at each visit with Visit 4A (120-180 days) prospectively identified as the primary point of interest. The upper bound of the two-sided 95% confidence interval will be compared to the margin, 0.1. If the upper bound is less than the margin, the null hypothesis will be rejected and the TNFT00 IOL will be concluded non-inferior to the 839MP IOL for UCDVA. The two-sided 95% confidence intervals will be reported for the difference between the treatment groups at each visit.

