## 4.2 Effectiveness Hypotheses

### 4.2.1 Primary Effectiveness Hypotheses

The primary objective is to demonstrate non-inferiority of the TFNT00 IOL to the 839MP IOL in mean photopic binocular uncorrected intermediate (60 cm) visual acuity (UCIVA) at Visit 4A.

The null and alternative hypotheses for the primary analysis are:

$$H_0: \mu_{\text{TFNT00VA}} - \mu_{\text{839MPVA}} \geq \Delta$$

$$H_A: \mu_{\text{TFNT00VA}} - \mu_{\text{839MPVA}} < \Delta$$

where,  $\Delta$  refers to the non-inferiority margin, set at 0.1 logMAR, and  $\mu_{\text{TFNT00VA}}$ ,  $\mu_{\text{839MPVA}}$ , refer to the mean binocular high contrast UCIVA for the test and control lenses, respectively.

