## 4.3 Statistical Methods for Effectiveness Analyses

### 4.3.1 Primary Effectiveness Analyses

The primary hypothesis will be tested by generating a two-sided 90% confidence interval based on least squares means using a repeated measures analysis of variance model. The variable 'visit' will be entered as a classification variable to avoid assumptions on the shape of the response. Two-sided 90% confidence intervals for the difference between treatment groups at each visit will be reported with Visit 4A prospectively identified as the primary time point of interest. The upper bound of the two-sided 90% confidence interval will be compared to the margin, 0.1. If the upper bound is less than the margin, the null hypothesis will be rejected and the TFNT00 IOL will be concluded to be non-inferior to the 839MP IOL for UCIVA. SAS pseudo-code for this model follows:

```
proc mixed data=uci_va order=internal noclprint;
class treatment visit subject;
model uci_va = treatment|visit / solution ddfm=kenwardroger;
repeated / type=un sub=subject(treatment);
lsmeans treatment / cl diff alpha=0.1;
run;
```

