### 4.3.2 Secondary Effectiveness Analyses

#### 4.3.2.1 Visual Acuity

For the superiority hypothesis tests, treatment group comparison for UCIVA will be made and the first secondary objective will be demonstrated if  $p < 0.025$  from a repeated measures analysis of variance. The variable 'visit' will be entered as a classification variable to avoid assumptions on the shape of the response. Tests will be conducted and two-sided 95% confidence intervals for the difference between treatment groups will be generated at each visit with Visit 4A prospectively identified as the primary time point of interest. For the fourth and fifth secondary objectives, superiority will be demonstrated if  $p < 0.05$  (or  $p < 0.025$ , depending on the gatekeeping) for UCNVA and UCDVA at Visit 4A, respectively. SAS pseudo-code for this model will be the same as for the primary effectiveness analysis with, for the first secondary objective, the change to  $\alpha = 0.05$  and for the fourth and fifth secondary objectives the change to  $\alpha = 0.05$  (if only one of the first or second secondary hypotheses is rejected) and  $\alpha = 0.1$  (if both the first and second secondary hypotheses are rejected). The multiple testing strategy is listed in more detail in Section 4.4.

For the non-inferiority hypothesis test of UCDVA, the second secondary objective, treatment group comparisons will be tested by generating a two-sided 95% confidence interval based on least squares means using a repeated measures analysis of variance model. The variable 'visit' will be entered as a classification variable to avoid assumptions on the shape of the response. Two-sided 95% confidence intervals for the difference between treatment groups at each visit will be reported with Visit 4A prospectively identified as the primary time point of interest. The upper bound of the two-sided 95% confidence interval will be compared to the margin, 0.1. If the upper bound is less than the margin, the null hypothesis will be rejected and the TFNT00 IOL will be concluded to be non-inferior to the 839MP IOL for UCDVA. SAS pseudo-code for this model will be the same as for the primary effectiveness analysis with the change to  $\alpha=0.05$ . The multiple testing strategy is listed in more detail in Section 4.4.

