For the non-inferiority hypothesis test of UCNVA, the third secondary objective, treatment group comparisons will be tested by generating a two-sided 90% (or 95%) confidence interval based on least squares means using a repeated measures analysis of variance model. The variable 'visit' will be entered as a classification variable to avoid assumptions on the shape of the response. Two-sided 90% (or 95%) confidence intervals for the difference between treatment groups at each visit will be reported with Visit 4A prospectively identified as the primary time point of interest. The upper bound of the two-sided 90% (or 95%) confidence interval will be compared to the margin, 0.1. If the upper bound is less than the margin, the null hypothesis will be rejected and the TFNT00 IOL will be concluded non-inferior to the 839MP IOL for UCNVA. SAS pseudo-code for this model will be the same as for the primary effectiveness analysis with, for the third secondary objective, the change to  $\alpha=0.05$  (if only one of the first or second secondary hypotheses is rejected) and  $\alpha=0.1$  (if both the first and second secondary hypotheses are rejected). The multiple testing strategy is listed in more detail in Section 4.4.

For the decision of which alpha is appropriate in the SAS code for the third, fourth and fifth secondary objectives, use the following logic:

If the first secondary objective (UCIVA superiority) is met, but the second secondary objective (UCDVA non-inferiority) is not met, use  $\alpha=0.05$ .

If the first secondary objective (UCIVA superiority) is not met, but the second secondary objective (UCDVA non-inferiority) is met, use  $\alpha=0.05$ .

If the first secondary objective (UCIVA superiority) is met and the second secondary objective (UCDVA non-inferiority) is met, use  $\alpha=0.1$ .

If the first secondary objective (UCIVA superiority) is not met and the second secondary

objective (UCDVA non-inferiority) is not met, the other secondary objectives will not be tested.

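### The SAP code for all six visual acuity tests returns the average of the Visit 3A and Visit 4A differences, while the SAP and protocol text test the difference at Visit 4A

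*SAP*

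**What the plan says.** The text of both documents puts the comparison at Visit 4A.

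- SAP 4.2.1 states the primary objective as non-inferiority "in mean photopic binocular uncorrected intermediate (60 cm) visual acuity (UCIVA) at Visit 4A".
- SAP 4.3.1 says that intervals for the "difference between treatment groups at each visit will be reported with Visit 4A prospectively identified as the primary time point of interest".
- Protocol 15.4.1.2 says: "The two sided 90% confidence intervals will be reported for the difference between the treatment groups at each visit". It also names Visit 4A as the primary time point.
- Protocol 15.4.2.2, on the secondary non-inferiority tests, says that "least squares means will be used to estimate the treatment effect at each visit with Visit 4A (120-180 days) prospectively identified" as primary.

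The code in SAP 4.3.1 fits `treatment|visit`, that is, both main effects and their interaction. Its only request for estimates is "lsmeans treatment / cl diff alpha=0.1". It contains no treatment-by-visit term in LSMEANS and no ESTIMATE or LSMESTIMATE statement.

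SAP 4.3.2.1 carries this code to the secondary tests. For distance non-inferiority: "SAS pseudo-code for this model will be the same as for the primary effectiveness analysis with the change to" a different alpha. For near non-inferiority: "SAS pseudo-code for this model will be the same as for the primary effectiveness analysis with, for the third secondary objective, the change to" one of two alphas. The three superiority tests are handled in the same way. Alpha is the only change named.

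Binocular UCIVA is measured at two visits. The step "Assess binocular uncorrected intermediate (60 cm) visual acuity" appears in protocol 12.1.5 (Visit 3A) and again in 12.1.6 (Visit 4A). Distance and near acuity are also measured at both.

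**The concern.** A least squares mean for a main effect, in a model that also contains the interaction, averages over the levels of the other factor with equal weight. With two visits in the data, the coded line therefore estimates the mean of the 1-month and the Visit 4A lens differences. It does not give the Visit 4A difference, and it gives none of the per-visit intervals that the text promises.

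Two other places in the SAP do not correct this. The success criterion in the Executive Summary refers to a least squares means difference without naming a visit, although the key objective just above it does. Footnote b of Table 4-2 describes the model as having terms for treatment and visit and omits the interaction.

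If the lens difference changes between 1 month and Visit 4A and the code is run as written, all six decisions test a different quantity from the one stated. The error can go either way: a false claim of non-inferiority or superiority, or a loss of power. No passage says whether text or code prevails.

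**Working it through.** **Inputs from the documents.** 76 subjects per arm and a common SD of 0.16 logMAR (SAP section 7); margin 0.1 logMAR; primary test at one-sided 5% (two-sided 90% interval, SAP 4.3.1 and protocol 15.4.1.2); first superiority test at 2.5%, taken as one-sided as SAP 4.4 states; planning difference of 0.09 logMAR for superiority (SAP section 7).

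**Assumptions, because the documents give no figure.** The SD of 0.16 applies at both visits; data are complete; the correlation ρ between a subject's Visit 3A and Visit 4A values lies between 0 and 0.9; the Visit 3A difference is varied. Write d3 and d4 for the true TFNT00 minus 839MP differences at Visits 3A and 4A.

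**The plan's own figures first.** For a comparison at a single visit, SE = 0.16 × √(2/76) = 0.0260. With a true difference of 0, the chance that the upper one-sided 97.5% limit is below 0.1 is 97.1% by the normal approximation and 96.9% by the noncentral t with 150 df. The plan states 98%. Power for a difference of 0.09 at one-sided 2.5% is 93.1%, in line with the stated figure of more than 90%. The stated power therefore fits a single-visit contrast.

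**What the coded line estimates.** In the treatment-by-visit cells, the treatment LS-means difference has coefficients +0.5, +0.5, −0.5, −0.5. It therefore estimates (d3 + d4)/2. The Visit 4A contrast has coefficients 0, +1, 0, −1 and estimates d4. A generalised least squares fit to simulated data (ρ = 0.6) confirmed this: visit differences of 0.0358 and 0.1182 gave a treatment LS-means difference of (0.0358 + 0.1182)/2 = 0.0770.

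**Standard errors.** The SE of the average is 0.0260 × √((1 + ρ)/2). For ρ = 0 this is 0.0184 and for ρ = 0.9 it is 0.0253, against 0.0260 at Visit 4A.

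**Consequences if the code is run as written.** Each probability comes from the noncentral t with 150 df. The noncentrality is (0.1 − (d3 + d4)/2)/SE for non-inferiority and −((d3 + d4)/2)/SE for superiority. Ranges run over ρ from 0 to 0.9.

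| Test and truth | d3 | d4 | Coded average | Visit 4A contrast |
|---|---|---|---|---|
| False non-inferiority, one-sided 5% | 0.05 | 0.10 | 25–39% | 5% |
| | 0.08 | 0.10 | 11–14% | 5% |
| | 0.10 | 0.10 | 5% | 5% |
| False superiority, one-sided 2.5% | −0.05 | 0 | 16–27% | 2.5% |
| | −0.02 | 0 | 6–8% | 2.5% |
| Non-inferiority power, one-sided 5% | 0.10 | 0 | 63–86% | 98.6% |
| Superiority power, one-sided 2.5% | 0 | −0.09 | 42–68% | 93% |

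In each range the high end belongs to ρ = 0, where the averaged SE is smallest. For the first row, ρ = 0, 0.5 and 0.9 give 38.6%, 29.5% and 25.4%; simulation with 40,000 trials per scenario gave 38.7%, 29.7% and 25.5%.

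**The case against.** The strongest reply is that the text settles the matter. Visit 4A is named in the key objective, the objectives, the hypothesis section and the method text for the acuity tests, and throughout the protocol. Neither document asks for an average over visits. The block is introduced as pseudo-code for the model, and the decision rule stands in the prose above it. The per-visit intervals that the text requires cannot be produced from the coded line, so a programmer would have to add the treatment-by-visit means, and the Visit 4A contrast would then be in the output.

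This has force. It makes harm less likely, but it does not remove the contradiction: the code cannot deliver what its own paragraph requires, and no rule of precedence is given. SAP 4.3.2.1 also tells the analyst which alpha to put in the SAS code for three of the secondary tests, so the code is meant to be used.

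The second reply is that the large error rates need large shifts between visits. That stands. The 25–39% needs the difference to double from 0.05 to 0.10, and the power losses need shifts of 0.09 and 0.10, which are the whole planning effect and the whole margin. Zero correlation between two measurements on one subject is also an extreme. With a shift of 0.02 and ρ of 0.5 to 0.9, false non-inferiority is 10.5–11.5% and false superiority 5.9–6.5%. Non-inferiority power with d4 = 0 and d3 = 0.02 is 97–99%, essentially unchanged from 98.6%.

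**Conclusion.** The code and the text specify different contrasts for all six tests, and the code is the one that departs from the stated hypotheses. The algebra rests on no assumption beyond two visits in the data, which the protocol's visit procedures confirm.

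The size is conditional. It arises only if the code is run as written and the lens difference changes between visits. Then a shift of 0.02 logMAR roughly doubles the non-inferiority error (5% to 11–14%) and more than doubles the superiority error (2.5% to 6–8%); a shift of 0.05 multiplies each by five or more. If the difference is constant, type I error is nominal, but the reported interval is still not the Visit 4A interval. The correlation and the Visit 3A differences are assumed, so these figures are illustrative.

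This should be fixed before unmasking, so that nobody has to choose between two readings of the primary analysis after seeing the results. The margin, the hypotheses and the sample size are not affected.

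**What to change.** In SAP 4.3.1, replace the LSMEANS line with `lsmeans treatment*visit / cl diff alpha=...` or an equivalent ESTIMATE or LSMESTIMATE statement. State there and in 4.3.2.1 that each of the six decisions uses TFNT00 minus 839MP at Visit 4A.

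Three small edits keep the rest consistent:

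- Write `repeated visit / type=un subject=subject(treatment)`. The coded REPEATED statement names no visit effect, so a subject whose Visit 3A row is absent would have the Visit 4A value placed in the first covariance position.
- Name the treatment-by-visit term in footnote b of Table 4-2.
- Add Visit 4A to the success criterion in the Executive Summary.

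The cost is one line of code and a few words of SAP text. No new data are needed and the sample size does not change.

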### 4.3.2 Secondary Effectiveness Analyses

#### 4.3.2.1 Visual Acuity

For the superiority hypothesis tests, treatment group comparison for UCIVA will be made and the first secondary objective will be demonstrated if  $p < 0.025$  from a repeated measures analysis of variance. The variable 'visit' will be entered as a classification variable to avoid assumptions on the shape of the response. Tests will be conducted and two-sided 95% confidence intervals for the difference between treatment groups will be generated at each visit with Visit 4A prospectively identified as the primary time point of interest. For the fourth and fifth secondary objectives, superiority will be demonstrated if  $p < 0.05$  (or  $p < 0.025$ , depending on the gatekeeping) for UCNVA and UCDVA at Visit 4A, respectively. SAS pseudo-code for this model will be the same as for the primary effectiveness analysis with, for the first secondary objective, the change to  $\alpha = 0.05$  and for the fourth and fifth secondary objectives the change to  $\alpha = 0.05$  (if only one of the first or second secondary hypotheses is rejected) and  $\alpha = 0.1$  (if both the first and second secondary hypotheses are rejected). The multiple testing strategy is listed in more detail in Section 4.4.

For the non-inferiority hypothesis test of UCDVA, the second secondary objective, treatment group comparisons will be tested by generating a two-sided 95% confidence interval based on least squares means using a repeated measures analysis of variance model. The variable 'visit' will be entered as a classification variable to avoid assumptions on the shape of the response. Two-sided 95% confidence intervals for the difference between treatment groups at each visit will be reported with Visit 4A prospectively identified as the primary time point of interest. The upper bound of the two-sided 95% confidence interval will be compared to the margin, 0.1. If the upper bound is less than the margin, the null hypothesis will be rejected and the TFNT00 IOL will be concluded to be non-inferior to the 839MP IOL for UCDVA. SAS pseudo-code for this model will be the same as for the primary effectiveness analysis with the change to  $\alpha=0.05$ . The multiple testing strategy is listed in more detail in Section 4.4.

For the non-inferiority hypothesis test of UCNVA, the third secondary objective, treatment group comparisons will be tested by generating a two-sided 90% (or 95%) confidence interval based on least squares means using a repeated measures analysis of variance model. The variable 'visit' will be entered as a classification variable to avoid assumptions on the shape of the response. Two-sided 90% (or 95%) confidence intervals for the difference between treatment groups at each visit will be reported with Visit 4A prospectively identified as the primary time point of interest. The upper bound of the two-sided 90% (or 95%) confidence interval will be compared to the margin, 0.1. If the upper bound is less than the margin, the null hypothesis will be rejected and the TFNT00 IOL will be concluded non-inferior to the 839MP IOL for UCNVA. SAS pseudo-code for this model will be the same as for the primary effectiveness analysis with, for the third secondary objective, the change to  $\alpha=0.05$  (if only one of the first or second secondary hypotheses is rejected) and  $\alpha=0.1$  (if both the first and second secondary hypotheses are rejected). The multiple testing strategy is listed in more detail in Section 4.4.

For the decision of which alpha is appropriate in the SAS code for the third, fourth and fifth secondary objectives, use the following logic:

If the first secondary objective (UCIVA superiority) is met, but the second secondary objective (UCDVA non-inferiority) is not met, use  $\alpha=0.05$ .

If the first secondary objective (UCIVA superiority) is not met, but the second secondary objective (UCDVA non-inferiority) is met, use  $\alpha=0.05$ .

If the first secondary objective (UCIVA superiority) is met and the second secondary objective (UCDVA non-inferiority) is met, use  $\alpha=0.1$ .

If the first secondary objective (UCIVA superiority) is not met and the second secondary

objective (UCDVA non-inferiority) is not met, the other secondary objectives will not be tested.

Summaries of logMAR visual acuity will also include two-sided 90% confidence intervals. A composite visual acuity endpoint comprising binocular uncorrected visual acuity at Distance (4 m) and Near (40 cm), separately for Visits 3A and 4A, will be summarized as a categorical variable with the following categories: 20/20 or better ( $\leq 0.04$  logMAR), 20/25 or better ( $\leq 0.14$  logMAR), 20/32 or better ( $\leq 0.24$  logMAR) and 20/40 or better ( $\leq 0.34$  logMAR). Both binocular uncorrected visual acuities (distance and near) will have to meet the threshold to be counted in a category.

[figure not shown]
To examine inter-site variation in outcome, forest plots of near, intermediate and distance visual acuity will be produced by plotting the difference in means and associated standard error for each site. Forest plots of near, intermediate and distance visual acuity for the difference in means and two-sided 90% CIs will also be produced.

